## 1. Study synopsis

APPLICANT / COORDINATING INVESTIGATOR	[name], PhD Department of Dermatology Medical University of Graz [name] [name], Austria [contact] Telefax: [contact] E-mail: [contact]
TITLE OF STUDY	The effect of antihypertensive drugs on severity of anaphylaxis and side-effects during venom immunotherapy
SHORT TITLE	EADOAS-Study
POPULATION	Patients with a history of anaphylactic sting reaction
OBJECTIVE(S)	The primary objective of this study is to evaluate whether subjects under antihypertensive treatment with beta-blockers and/or ACE-inhibitors show more side effects during VIT compared to subjects with no antihypertensive treatment.
INTERVENTION(S)	Venom immunotherapy (VIT)
KEY INCLUSION AND EXCLUSION CRITERIA	Inclusion criteria: Subjects aged from 35 to 85 years with a history of anaphylactic sting reaction  Exclusion criteria (only for phase 2): Absolute contraindications for VIT, Pretreatment with Omalizumab
OUTCOME(S)	Proportion of side-effects during venom immunotherapy
STUDY TYPE	Prospective multicenter observational study
STATISTICAL ANALYSIS	The primary analysis will compare the proportion of objective side effects between the groups (subjects under antihypertensive treatment vs. subjects without antihypertensive treatment) using a Mantel-Haensel estimate of the odds ratio stratified by clinic.  A logistic regression model will be used to control for other possible confounders
ETHICAL APPROVALS	Participating study centers have to obtain ethical approvals from their institutional review boards.
SPONSORING	Unrestricted grants from pharmaceutical companies
SAMPLE SIZE	1319
TRIAL DURATION	July 1, 2014 – December 31, 2019 (End of inclusion phase: January 31, 2018)

PARTICIPATING CENTERS	Name	Address	Country
	[name] [name], MD, PhD	Department of Dermatology Medical University of Graz [name] [name], Austria	Austria
	[name], MD	Clinical Department of Dermatology Medical University of Innsbruck [name] [name], Austria	Austria
	[name]	Department of Dermatology SALK Paracelsus Medical University Salzburg [name] [name], Austria	Austria
	Prim. Univ.-Doz. [name]	Department of Dermatology Elisabethinen Hospital Linz [name] [name], Austria	Austria

## 2. Indication

There is an ongoing debate whether antihypertensive treatment with beta-blockers and/or ACE-inhibitors comprises a risk factor for more severe anaphylactic reactions due to insect stings. Side effects under venom immunotherapy (VIT) could be more severe and more frequent. In the literature, data are controversial and originate from case reports or statistically underpowered studies.

## 3. Introduction

Since the introduction of beta-blockers in the early 1960s and the availability of ACE-inhibitors in the early 1980s, there is an ongoing discussion about negative effects of those substances on allergic reactions and side-effects during allergen immunotherapy. Although there is a theoretical and anecdotal clinical evidence for possible interactions, data of studies are controversial and their role as risk factors is a debated issue. All available studies have drawbacks and are underpowered. Therefore, current recommendations are practice-oriented but not sufficiently evidence-based. To stop the endless debate, a well planned multicenter study is needed.

### 3.1 *Beta-blockers*

Beta-blockers are mostly used to treat arterial hypertension and are valuable drugs in the treatment of cardiovascular disease. However, they are also prescribed for non-cardiac conditions like migraine prophylaxis or symptomatic treatment of skeletal muscle tremor.

#### 3.1.1 Background

Four main types of adrenergic receptors ( $\alpha_1$ ,  $\alpha_2$ ,  $\beta_1$ ,  $\beta_2$ ) can be roughly distinguished according to their affinity to norepinephrine and epinephrine. In brief, stimulation of  $\beta_1$  receptors induces a positive chronotropic and inotropic effect on the heart as well as a renin release of the kidney.  $\beta_2$  stimulation results in dilatation of blood vessels and bronchioles, and  $\alpha_2$  stimulation induces contraction of blood vessels and bronchioles . Basically,  $\beta$  blockade inhibits the effect of both endogenously released and therapeutically administered epinephrine on  $\beta$  receptors in case of anaphylaxis. Therefore epinephrine treatment can be ineffective or due to the block of  $\beta_1$  and  $\beta_2$  actions may facilitate unopposed  $\alpha$ -adrenergic effects like bronchoconstriction and bradycardia .

### 3.1.2 Potential effect on immunotherapy

- *Side effects do not appear to be more frequent, but maybe more serious*
- *Side effects could be refractory to treatment*
- *Emergency treatment may cause paradoxical treatment effects*

Both beta blockers and allergen immunotherapy are frequently prescribed, therefore allergists commonly encounter patients who are candidates for immunotherapy and are treated with beta blockers. Fatality studies have shown that particularly elderly patients with pre-existing cardiovascular disease die from hymenoptera venom allergy. Therefore unlike for respiratory allergies, immunotherapy with hymenoptera venoms is commonly performed in elderly patients who are more likely to be on beta blocker treatment.

The risk of beta blocker treatment is still questionable. There is plenty of experimental human and animal studies mainly performed in the 1970s and 80s as well as anecdotal clinical evidence that anaphylaxis may be influenced by pharmacodynamics of  $\beta$ -blockade. In theory,  $\beta$ -blockade perturbs the control of endogenously produced mediators of anaphylaxis resulting in an enhanced generation, release, and reduced effects of these mediators on the end organs. If anaphylaxis occurs in a patient on beta-blocker, it may therefore be more severe and protracted. There is also evidence that even beta-blocker eye drops have systemic effects. However, the plurality of uncontrolled variables makes the susceptibility of individual patients to this effect of topically and orally applied beta-blockers largely unpredictable. The second point is that emergency treatment with epinephrine may be ineffective or promote undesired  $\alpha$ -adrenergic and vagotonic effects.  $\beta$ -blockade dramatically alters pharmacotherapeutic actions of epinephrine and isoproterenol, as up to 80-fold higher doses may be necessary. Additionally, the block of  $\beta_1$  and  $\beta_2$  actions of epinephrine may facilitate unopposed  $\alpha$ -adrenergic and reflex vagonotonic effects, which can result in increased mediator release, bronchoconstriction and bradycardia. The pronounced  $\alpha$ -receptor activation in the presence of epinephrine may also constrict coronary arteries or exaggerate systemic pressor effects of epinephrine leading to severe hypertensive episodes.

There are three clinical studies dealing with the question whether patients taking beta-blockers are at increased risk of having side effects during immunotherapy. Hepner et al prospectively studied 3178 patients; 68 patients were taking beta-blockers. Although statistically 3 patients were expected to have systemic reactions, only one patient taking a beta-blocker had a systemic reaction. In a retrospective study of Mueller et al, 1389 patients were included, and 25 patients were on beta-blockers during immunotherapy. They also did not find an increased incidence of systemic reactions, and reactions were not more severe than in the control group. Most recently, an EAACI observational prospective multicenter study on 680 patients (15 on beta-blockers) could not identify beta-blocker therapy as independent predictor for an emergency intervention during immunotherapy. Interestingly, in a former EAACI observational study on 962 patients (52 on beta-blockers) beta blocker were not identified as independent risk factor for severe anaphylaxis, which

was consistent with a large Australian study. In this study, case records of 1149 patients were retrospectively analyzed. Univariate analyses suggested that reaction severity was influenced by beta-blockers. However, in the multivariate analysis beta-blockers were not identified as independent risk factor. Recently, 657 patients suitable for VIT were included in a large single-center observational study. 59 were on beta-blocker treatment; 27 on both, ACE-inhibitors and beta blockers. Again, beta blockers were not identified to be correlated with severe anaphylaxis. More recently, again controversial data have been published: Beta-blockers were not associated with severe anaphylactic symptoms such as syncope or hypotension, but with 3 or more organ involvement and hospitalization.

### 3.1.3 Current recommendations

There is good evidence in the literature that anaphylaxis is not more frequent in patients receiving beta-blockers. On the other side patients may be at increased risk from more severe systemic reactions and from ineffective emergency treatment. Therefore there is still a relative contraindication for beta blockers in subjects allergic to hymenoptera venom.

## 3.2 ACE-inhibitors

ACE-inhibitors are primarily used to treat arterial hypertension and congestive heart failure.

### 3.2.1 Background

The renin angiotensin aldosterone system (RAS) regulates blood pressure. The system in general increases blood pressure by reduced salt and water excretion and vasoconstriction if blood pressure acutely drops. ACE inhibitors block conversion of angiotensin I to angiotensin II, which results in vasodilatation and reduced blood volume. Therefore, hypotension during anaphylaxis may not sufficiently counteracted by the inhibited RAS.

### 3.2.2 Potential effect on immunotherapy

- *Diminished ability to counteract allergy-induced hypotension*

There is some anecdotal clinical evidence that a subset of patients receiving venom immunotherapy tend to have more serious hypotension in case of side effects. In theory, the RAS is part of the compensatory physiologic response to anaphylaxis and thus ACE-inhibitors may hamper an effective response in some instances of anaphylaxis. However, also a dysfunctional RAS in which overall RAS activity is diminished might aggravate symptoms due to an insufficient response to anaphylaxis.

The role of ACE-inhibitors as risk factor for more severe anaphylaxis is still a debated issue. In a large Australian retrospective analysis done by Brown, 1149 patients who have had anaphylaxis were included. Among these, fifty-seven patients were on ACE-inhibitor treatment. Multivariate analysis did not identify ACE-inhibitors as independent risk factor. However, in an EAACI observational prospective multicenter study on 962 patients with hymenoptera allergy, the 42 patients receiving ACE inhibitors had an approximately 2.3-fold increased risk for severe anaphylaxis (odds ratio 2.26, 95% CI 1.13 - 4.56).

The second EAACI observational multicenter study on 680 VIT patients (18 patients on ACE-inhibitors) did not identify ACE-inhibitors as independent risk factor for side effects.

Recently, 657 patients suitable for VIT were included in a large single-center observational study. 32 were on ACE and 27 on beta-blocker treatment. Again, ACE-inhibitors were not identified to be correlated with severe anaphylaxis. Another retrospective analysis revealed that ACE-inhibitors were not associated with severe anaphylactic symptoms such as syncope or hypotension, but with 3 or more organ involvement and hospitalization. Most recently, in a study on 743 patients (thereof 90 on ACE inhibitor treatment) ACE inhibitors did not increase the frequency of side-effects during the buildup phase of VIT.

### 3.2.3 Current recommendations

If ACE-inhibitors increase the risk of more serious anaphylaxis is still a debated issue. Currently, the recommendation that patients receiving ACE-inhibitors are more likely to have side effects during immunotherapy is only based on case reports. Nevertheless, until there will not be new evidence, current guidelines recommend to replace ACE-inhibitors, if feasible.

## 4. Justification of the study

Although a considerable number of studies on this topic were performed, all studies were underpowered to identify beta blockers and/or ACE inhibitors as risk factors. The number of included patients was usually high; however, the proportion of patients on antihypertensive treatment was low ranging from 2-11%. In the current study we plan to enroll 1319 patients aged 35-85. Considering retrospective data from our own institution it is assumed that 24% (317) will be on beta blockers and/or ACE inhibitors. Based on these data, a clear statement on the risk of antihypertensive treatment will be possible.

## 5. Study criteria

### 5.1 Primary objective

- The primary objective of this study is to evaluate whether subjects under antihypertensive treatment with beta-blockers and/or ACE-inhibitors show more side effects during VIT compared to subjects with no antihypertensive treatment.

### 5.2 Secondary objectives

- To evaluate whether subjects under antihypertensive treatment with beta-blockers and/or ACE-inhibitors have more severe sting reactions.
- To correlate the prevalence of cardiovascular diseases and/or hypertension with the risk for more severe systemic sting reactions and with more severe and more frequent side effects under VIT.
- To evaluate whether bee venom is associated with a higher frequency of side-effects.
- To evaluate whether high sIgE levels are correlated to a higher frequency of side-effects.
- To evaluate whether high tryptase levels are correlated to a higher frequency of side-effects.
- To evaluate whether quicker up-dosing protocols are correlated to a higher frequency of side-effects.
- To evaluate efficacy of VIT by sting challenges or field stings and look for differences between patients with and without antihypertensive treatment

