### 6.4.5 Venom immunotherapy (VIT)

There is no standard buildup phase; centers use their own standard protocols. Typically, conventional (outpatient), Cluster/Ultrarush- (partial inpatient) and Rush-protocols (inpatient) will be performed. The respective venom that is used for VIT will be recorded (bee or wasp venom, trade name, company). Injections will be administered subcutaneously in the dorsal part of the upper arm, one hand's breadth above the elbow, or in the volar part of the thigh. All interventions will be performed according to the in-house protocols of participating centers.

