## 7. Overall study design and plan

The study is conducted as an open, prospective observational study on an outpatient basis. After giving the Informed Consent subjects will be screened at Visit 1. Subjects meeting the inclusion and exclusion criteria will be included (phase 1). If subjects agree to receive VIT, side effects during the buildup phase will be recorded (phase 2). At the first annual control visit side effects during maintenance phase and, if applicable, the outcome of field stings of sting challenge tests will be recorded (phase 3). No additional study-related visits are required.

Participation in this study will have no influence on decision-making for venom-immunotherapy. All procedures have to be in concordance with current EAACI guidelines, and will be conducted individually by each study center.

Detailed schedule of events please see Table 2.

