***Phase 3 (maintenance phase) – Visit 3b/3c optional***

- Document field stings and sting challenges
- Record outcome of field sting or sting challenge

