### **11.2 Analysis of secondary endpoints**

For the analysis of secondary endpoints, comparison between groups will be made by using  $\chi^2$  statistics or the Fisher exact test for categorical variables and by t-test or the Mann-Whitney U test for continuous variables.

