## **12. Regulatory and ethical obligations**

### **12.1 *Institutional Review Board***

Each study center will follow the respective regulations of the local ethical review board. Approval of the study seems necessary particularly with respect to the statistical evaluation of patient data, which have to be processed in an anonymized form. Only routine diagnostic procedures will be performed. No additional diagnostic test, treatment or check of efficacy with sting challenges will be done solely for the study

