**13.2 Table 2**

Study procedures	Visit 1	Visit 2	Visit 3/3a	Visit 3b/c a
	Screening/Inclusion	Up-dosing	Maintenance Phase	Field sting / sting challenge
Informed consent	X			
Inclusion/Exclusion review	X			
Allergy history	X			
Medical history / co-medication	X	X	X	X
Demographics	X			
Collect results of IDT and CAP	X			
Recording of decision regarding venom immunotherapy (yes/no)	X			
Recording of venom used for VIT		X		
Recording of side-effects		X	X	
Recording of stinging insect				X
Recording of sting reaction				X

a if applicable.

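### The comparison of VIT efficacy between drug groups has no rule for sting type or insect match, so the unadjusted test in section 11.2 would be biased if the sting mix differed by group

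*Combined protocol and SAP*

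**What the plan says.** The last secondary objective in section 5.2 is "To evaluate efficacy of VIT by sting challenges or field stings and look for differences between patients with and without antihypertensive treatment". It puts one efficacy question to two sources of evidence.

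The data come from the optional part of phase 3 in section 8, headed "Visit 3b/3c optional", where the instruction is "Record outcome of field sting or sting challenge". Table 2 (section 13.2) gives both sources one shared column, marked as applying only where relevant, and includes the row "Recording of stinging insect". Section 6.4.5 adds: "The respective venom that is used for VIT will be recorded (bee or wasp venom, trade name, company").

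On who is challenged, section 12.1 says: "No additional diagnostic test, treatment or check of efficacy with sting challenges will be done solely for the study".

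For secondary endpoints, section 11.2 names chi-square "statistics or the Fisher exact test for categorical variables", and a t-test or Mann-Whitney test for continuous ones. Stratification by center and a logistic model appear only in section 11.1, for the primary endpoint, and that covariate list contains neither sting type nor stinging insect. Section 11 bases the analyses on patients who completed buildup. No subset of stung patients, and no definition of protection or failure, is given.

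**The concern.** Drug exposure is not randomised here, and neither is the kind of sting that tests the treatment. Two features of a sting could affect whether a reaction follows, whatever the drug: whether it was a challenge or a field sting, and whether the insect matches the venom used for VIT. A sting by an insect that the venom does not cover says little about the treatment given.

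The plan documents what is needed to handle both features but gives them no role in the comparison. Because challenges follow routine practice at each center and not study assignment, the mix of stings could differ between patients with and without antihypertensives. A crude test would then combine the drug contrast with a contrast in sting type and insect match. At stake is a statement that VIT protects better, worse or equally well in patients on these drugs.

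**Working it through.** **The plan's own figures.** Section 11.3 concerns side effects, not sting outcomes. It reproduces: 631 and 200 patients with 6% and 12.3% give 79.96% power (stated 80%); the odds ratio is (0.123/0.877)/(0.06/0.94) = 2.197 (stated 2.2); retention is 0.70 × 0.90 = 0.63, and 831/0.63 = 1319.05 (stated 1319). No sting count, reaction rate or power is given for the efficacy comparison. From section 11.3 I therefore take only the group sizes, as an upper bound on patients stung.

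**Inputs that must be assumed.** The reaction risks p_A and p_B for two kinds of sting, and the share s of kind A in each drug group. A and B can be read as challenge and field sting, in either order, or as insect covered and not covered. In the first two cases below the drug has no effect within either kind.

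**Formula.** Crude rate = s × p_A + (1 − s) × p_B. Crude OR = odds with the drugs / odds without.

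**Stronger case** (12% vs 4%; A makes up 25% of stings with the drugs, 60% without)
- With the drugs: 0.25 × 0.12 + 0.75 × 0.04 = 0.060
- Without: 0.60 × 0.12 + 0.40 × 0.04 = 0.088
- OR = (0.060/0.940)/(0.088/0.912) = 0.66

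**Milder case** (8% vs 5%; 40% vs 60%)
- With the drugs: 0.40 × 0.08 + 0.60 × 0.05 = 0.062
- Without: 0.60 × 0.08 + 0.40 × 0.05 = 0.068
- OR = (0.062/0.938)/(0.068/0.932) = 0.91

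Swapping the mixes inverts these to 1/0.66 = 1.51 and 1/0.91 = 1.10. With the same mix in both groups the OR is 1.0.

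**Masking a real difference.** Assume a true OR of 2.2 within each kind, risks of 15% and 5% without the drugs (so 28.0% and 10.4% with them), and A making up 70% of stings without and 30% with.
- Without: 0.70 × 0.15 + 0.30 × 0.05 = 0.120
- With the drugs: 0.30 × 0.280 + 0.70 × 0.104 = 0.157
- Crude OR = 1.36

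With a 50/50 mix in both groups the crude OR would be 2.13, so nearly all of the loss comes from the mix.

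**False rejection by the unstratified 5% test** (normal approximation). Stronger case, all 831 stung:
- pooled rate (631 × 0.088 + 200 × 0.060)/831 = 0.0813
- standard error 0.0222 under the null and 0.0202 under the alternative
- (0.028 − 1.96 × 0.0222)/0.0202 = −0.76, giving 22%

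| Assumed patients stung | Stronger case | Milder case |
|---|---|---|
| All 831 (upper bound) | 22% | 5.5% |
| A quarter (about 158 and 50) | 7.5% | 4.8% |

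**Bias against noise.** With a quarter stung, the stronger case expects 50 × 0.060 = 3 events with the drugs and 158 × 0.088 = 13.9 without. The standard error of the log OR is √(1/3 + 1/47 + 1/13.9 + 1/143.9) = 0.66, against a bias of ln 0.66 = −0.41. At that size sampling error exceeds the bias.

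**The case against.** The strongest reply is that the plan is silent, not wrong. No section says that challenges and field stings will be pooled, or that a sting by an uncovered insect will count. Venom and insect are recorded, so the analyst could match them. A reader might infer that the plan adopts pooling of any sting by any insect. That goes further than the text: it is an inference from a single either-or objective, unadjusted tests and the absence of a restriction.

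A reader might also infer that clinicians hold back challenges from patients on these drugs. The documents do not show this. Section 3.1.3 calls beta-blockers a relative contraindication and section 3.2.3 reports guideline advice on ACE-inhibitors, but neither mentions sting challenges. Section 12.1 says only that challenges are not added for the study, and center routine alone need not produce a difference by drug. Every rate above is assumed. The objective is secondary, rests on optional visits and carries no power claim.

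These points limit the size and certainty of the concern, and they stand. They do not remove it. The only method stated for this comparison is a crude test in a non-randomised contrast, and leaving the sting rule open lets it be chosen after the data are seen.

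**Conclusion.** The concern holds as a conditional one. The plan leaves sting type and insect match out of the efficacy comparison and prescribes an unadjusted test. Bias follows only if the sting mix differs by drug group and reaction risk differs by sting type or insect. A difference in mix is possible because the study does not control who is challenged, but the documents give no figure for either condition.

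Direction and size are therefore unknown. Under the assumed rates with no true effect, the crude odds ratio runs from about 0.91 to 0.66, or from 1.10 to 1.51 if the mix is reversed. A false significant result becomes noticeable only in the stronger case with most patients stung; with few stung, imprecision is the larger problem. It would be wrong to conclude that the planned comparison is known to be biased, or biased in a particular direction. The primary analysis and the sample size are not affected. The point should be settled before analysis because a better method uses largely planned data and costs little.

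**What to change.** In section 11.2, add for this objective:

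1. Main analysis: only stings by the insect covered by the patient's VIT venom. List stings by other or unidentified insects separately.
2. Each patient counts once. State in advance which event is used if both a challenge and a field sting occur, since Visits 3b/3c do not exclude this.
3. Estimate the drug-group odds ratio by Mantel-Haenszel stratified by sting type, and by center where numbers allow, or by a logistic model with sting type and center. Show the challenge and field-sting results separately.
4. Report, per drug group, how many VIT patients were challenged, field-stung or not stung.

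Mantel-Haenszel is already the primary method in section 11.1, and center matters because challenges follow center routine.

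Costs: the main efficacy count becomes somewhat smaller, and the CRF must capture sting type. Section 8 makes that likely, but Table 2 has no row for it and the CRF is not among the documents, so this needs checking. The change does not deal with confounding by age or cardiovascular disease, which section 11.1 addresses for the primary endpoint only; the report should say so.
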